## **9.0 Study Withdrawal/Discontinuation**

Patients will be followed after transplantation. Individuals may withdraw from the study at any time by notifying one of the study investigators. Withdrawal from the study will be noted in the database. Following withdrawal, no subsequent blood collections for study

purposes will be obtained, and no further clinical information will be collected for this study.

In addition, the investigator has the right to withdraw a patient from the trial for any of the following reasons:

-protocol violation

-non-compliance

-any condition which, in the opinion of the investigator, might interfere with study objective

-any reason which, in the opinion of the investigator, adds additional risk to the patient

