### *Sources of materials- Patients*

Study participants who have given informed consent will undergo standard of care evaluations or study visits at either the Outpatient Transplant Unit, the inpatient Myelosuppression Unit, or the Clinical Research Center (CRC) at Vanderbilt University Medical Center. Two oral glucose tolerance tests and 1 hyperglycemic clamp will be performed on separate days prior to transplant and then each procedure will be repeated once between day+80 to day+100 (+/- 10 days) after transplant (Figure 5). In addition to the 6 research visits, study blood will be obtained at the following timepoints: pre-transplant (prior to beginning chemotherapy), Day+10, Day+20, Day+30, and Day+90 (all +/- 7 days) (the day of stem cell infusion is considered Day 0). A total of 550 mL of blood will be collected from the patient over approximately 110 days (over 3 to 4 months). Blood will be drawn for research purposes at the same time as routine blood sampling when feasible. Venous blood will be obtained by accessing the central venous catheter using sterile technique or via peripheral venipuncture. Samples will be coded with a unique alphanumeric identifier at the time of collection so that patient identity will be available only to study investigators and research staff. Clinical information, outcomes, and research data will be obtained by patient interview, medical chart review, and from laboratory testing. Information will be stored in a password-protected electronic database.

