#### *Diagnosis of PTDM*

PTDM is defined by the occurrence of a fasting blood glucose level  $\geq 126$  mg/dL or a random blood glucose level  $\geq 200$  mg/dL at any point from day +1 (day after stem cell infusion) to day +100 after transplant. Fasting blood glucose level will be assessed weekly during routine outpatient visits from day 1 to day 100 after transplant. Patients will be evaluated following an 8 hour overnight fast (water and medications allowed) during standard of care visits. Random blood glucose levels from day +1 to day +100 after transplant will be assessed during standard of care visits or during hospitalization. For hospitalized patients and patients receiving total parenteral nutrition (TPN), all blood glucose determinants will be considered random blood glucose levels for purposes of analysis.

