## **10.0 Statistical Considerations**

### **10.1 Power Analysis and Sample Size Calculation**

#### **D.3.c. Sample size calculation for Aims 1 and 2.**

$\beta$ -cell function, glucagon suppression, and IL-33 signaling are the primary outcomes for the aims. Sample size was calculated using a 2-group t-test with PS Software (version 3.0, Dupont&Plummer, 2009) at a 0.05 two-sided significance level. We estimate a 50% incidence of PTDM by day+100 (1, 8, 14). The sample size provides at least 80% power to detect a biologically meaningful difference in mean between patients with and without PTDM for each aim. The same patient cohort will be monitored for all aims. We will enroll 34 patients to ensure at least 80% power for each aim. Assuming the dropout rate is about 10% (early death or pre-HCT diagnosis of diabetes by OGTT), an additional 6 subjects will be recruited (41-43). Forty subjects are feasible to accrue over 4 years, given that 151 patients underwent allogeneic HCT at Vanderbilt in 2015.

**Subaim 1A primary outcome: second-phase GSIS.** A mean difference of 7.5  $\mu$ U/mL represents a significant difference in second-phase insulin release between healthy controls and individuals at risk for type 2 diabetes (44-46). A sample size of 17 patients in each group (either with or without PTDM) has 80% power to detect at least a 7.5  $\mu$ U/mL difference in insulin secretion between groups using a standard deviation of 7.5  $\mu$ U/mL.

**Subaim 1B primary outcome: glucagon secretion during OGTT.** AUC was calculated for each patient to present as total glucagon secretion during OGTT. Our preliminary data observed  $8.83 \pm 0.73$  pg/mL•min (mean  $\pm$  SD) in log(AUC) scale for patients with PTDM (Figure 4). With a sample size of 9 each group, there is 80% power to detect a log(AUC) change of from 8.83 pg/mL•min to 7.83 pg/mL•min.

**Aim 2 primary outcome: IL-33 signaling** Extrapolating our preliminary and pre-clinical data, a mean difference of 70 pg/mL is likely to represent a significant difference in IL-33 signaling between groups (14, 20). With a sample size of 17 in each group, there is 80% power to detect a 70 pg/mL difference in IL-33 production between groups using a standard deviation of about 70 pg/ml.

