## 10.2 Statistical Analysis Plan

### *Primary analysis of Subaim 1A*

We will compare pre-transplant insulin secretion (first- and second-phase GSIS) among patients who do or do not go on to develop PTDM. Wilcoxon rank sum test will be applied to compare the population mean difference between these two groups.

Multivariable logistic regression will evaluate whether GSIS is an independent predictor of PTDM after adjusting for the following covariates: gender, conditioning (ablative vs. reduced intensity), or acute GVHD requiring steroids. The estimated OR and 95% CI of the OR will be provided to measure the effect of the association. We will take a similar approach for the primary analysis of Aims 1B and 2 which will compare post-transplant total glucagon secretion during the OGTT ( $AUC_{Glucagon0-120}$ ) and serum IL-33 levels among patients with or without PTDM, respectively.

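### The withdrawal rule ends chart data collection along with study procedures, so patients still PTDM-free when withdrawn lose a Subaim 1A outcome that routine care goes on generating

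*Combined protocol and SAP*

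**What the plan says.** **Withdrawal (Section 9.0).** Participants may withdraw at any time. The rule continues: "Following withdrawal, no subsequent blood collections for study" purposes will be obtained, and "no further clinical information will be collected for this study". A new paragraph adds that "the investigator has the right to withdraw a patient from the trial for any of the following reasons": protocol violation, non-compliance, a condition that might interfere with the study objective, or added risk. That paragraph has no data rule of its own.

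**Source of the outcome (Section 6.0, Diagnosis of PTDM).** PTDM is a qualifying fasting or random glucose at any point from day +1 to day +100. "Fasting blood glucose level will be assessed weekly during routine outpatient visits from day 1 to day 100 after transplant". "Random blood glucose levels from day +1 to day +100 after transplant will be assessed during standard of care visits or during hospitalization". Under Sources of materials for patients, chart review is already a data source: "Clinical information, outcomes, and research data will be obtained by patient interview, medical chart review, and from laboratory testing".

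**Analysis (Section 10.2).** The Subaim 1A primary analysis compares pre-transplant insulin secretion "among patients who do or do not go on to develop PTDM". A logistic model adjusts for gender, conditioning and acute GVHD requiring steroids.

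**Dropout allowance (Section 10.1).** The plan needs 34 patients, assumes about 10% dropout and recruits six more. The causes named are "early death or pre-HCT diagnosis of diabetes by OGTT".

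**The concern.** For Subaim 1A, a patient's research contribution is complete once the pre-transplant clamp is done. All that remains is to learn whether PTDM occurs by day +100, and routine care produces that information whether or not the patient attends further research visits. A rule that ends chart collection together with procedures gives up the grouping variable of a primary analysis for no scientific gain.

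The loss is one-sided. A diagnosis already in the database stays there, so only patients still PTDM-free at withdrawal end up with unknown status. Some of them would have gone on to PTDM and some would not. At stake are a possible bias in the PTDM versus no-PTDM comparison and, to a lesser degree, power. Steroid-treated acute GVHD, a covariate in the logistic model, would also go unrecorded after withdrawal.

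**Working it through.** **1. Which patients are affected.** Setting Section 9.0 beside the PTDM definition gives three cases for a patient withdrawn after the clamp:

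| State at withdrawal | PTDM status available to the analysis |
|---|---|
| PTDM already recorded | Known, kept |
| PTDM-free, would develop it by day +100 | Unknown |
| PTDM-free, would remain so | Unknown |

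The prospective cohort in Section 3.0 had a median onset of day 23 among 50 cases. About half of diagnoses therefore came after that day, and a patient withdrawn PTDM-free in the first weeks cannot be assumed to stay so.

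**2. Why neither default is safe.**

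- *Counted as no PTDM:* later converters are misclassified and the difference shrinks. As an illustration, take 36 evaluable patients, truly 18 and 18, with two future converters withdrawn before onset. The groups become 16 and 20, and 2 of the 20 are misclassified. The expected difference falls from 7.5 to 7.5 × 18/20 = 6.75 µU/mL, if those two resemble other PTDM patients.
- *Dropped:* the retained PTDM group is tilted towards early onset, and the observed PTDM proportion is distorted. The comparison of means is biased if onset time or the chance of withdrawal is related to insulin secretion. The documents neither show nor exclude this.

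Section 10.2 does not say which approach applies.

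**3. Reproducing the plan's sample size.** Inputs from Section 10.1: difference 7.5 and SD 7.5 µU/mL, so d = 7.5/7.5 = 1; two-sided α 0.05; 50% PTDM, so a 1:1 split. For a two-sample t-test, df = n1 + n2 − 2, noncentrality = d·√(n1·n2/(n1 + n2)), and power is the probability that the noncentral t exceeds the 0.975 critical value in absolute size. Solving for 80% gives n = 16.7, so 17 per group. The planned figure reproduces.

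**4. The recruitment margin.** 34/0.90 = 37.8, so 38 would cover 10% dropout. The plan recruits 40; six of 40 is 15%. At 10%, 4 of 40 are lost to the named causes and 36 remain.

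**5. Power by assumed number of post-clamp losses.** The documents give no withdrawal rate, so the losses are assumptions.

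| Losses | Evaluable | Split | Noncentrality | t-test power |
|---|---|---|---|---|
| 0 | 36 | 18/18 | √9.00 = 3.000 | 83.0% |
| 2 | 34 | 17/17 | √8.50 = 2.915 | 80.7% |
| 3 | 33 | 16/17 | √8.24 = 2.871 | 79.4% |
| 4 | 32 | 16/16 | √8.00 = 2.828 | 78.1% |
| 6 | 30 | 15/15 | √7.50 = 2.739 | 75.3% |

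The illustration in step 2 has d = 6.75/7.5 = 0.9 and groups of 16 and 20. Noncentrality is 0.9 × √(320/36) = 2.683, and power is about 74%, treating the SD as unchanged. Two converters miscounted as PTDM-free thus cost more than two patients dropped evenly from the groups (80.7%).

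Section 10.2 names the Wilcoxon rank sum test for this comparison, not the t-test used for sizing. With normal data and d = 1, simulated power is about 80% at 18/18, 78% at 17/17 and 75% at 16/16, so the margin at 36 is thinner under the planned test.

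**The case against.** **Investigator withdrawal is not explicitly covered.** The data-stop sentence closes the paragraph on participants who withdraw themselves; the investigator's right follows separately. This stands as a limit. The unqualified wording makes coverage of both the natural reading, and nothing elsewhere overrides it, but it is not spelled out.

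**Stopping collection may be a matter of consent.** This stands for full withdrawal of consent, where ending collection is proper. It does not reach investigator withdrawal, or a participant who only wants to stop procedures. The consent form is not available for review, so it may already permit chart follow-up.

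**Power has a cushion.** A reader might infer from the 34 required that one withdrawal takes the study below 80%. The documents do not support that: 40 are recruited, and at 10% dropout two post-clamp losses are absorbed under the t-test. The single-loss reading holds only if all six extra patients have already gone to other causes.

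**Every withdrawal loses the outcome.** A reader might infer this too. It is wrong, because a recorded diagnosis is retained.

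**Bias is not demonstrated.** A reader might go on to say that sicker patients are withdrawn more often, or that one missed visit leads to withdrawal. The first is plausible for six research visits after a transplant, but no figure in the documents supports it. The second is not in the text: the ground given is non-compliance, and its use is discretionary.

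**Conclusion.** The point holds as a cheap improvement. Section 9.0 states a rule that, if followed, discards an obtainable Subaim 1A outcome for patients who are PTDM-free when withdrawn, and the analysis plan does not say how unknown status is handled. The main issue is possible bias from one-sided loss. Its size and direction cannot be fixed from the documents, and it could be nil if nobody is withdrawn between the clamp and day +100.

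The power effect is secondary. It runs from 83.0% with no losses to 75.3% with six, crossing 80% at the third. These figures assume d = 1, a near 1:1 split, 10% lost to the named causes and the t-test. The benefit is mainly for Subaim 1A: the Subaim 1B primary outcome needs the post-transplant OGTT, which chart review cannot replace.

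**What to change.** In Section 9.0:

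- Separate stopping study procedures from withdrawing consent to data use, and state which data rule applies to investigator withdrawal.
- After investigator withdrawal, or when a participant stops procedures but agrees to chart review, continue to collect routine glucose values, steroid and GVHD data, and survival from the chart to day +100.
- End collection only on full withdrawal of consent, and record the type and date of each withdrawal.

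In Section 10.2, state how patients with unknown PTDM status at day +100 are analysed. One option is to exclude them from the primary comparison and report sensitivity analyses that assign them first all to PTDM and then all to no PTDM. In Section 10.1, say whether the dropout allowance is meant to cover withdrawals.

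The cost is protocol wording and possibly a consent form amendment. No new visits or tests are needed, since chart review is already planned.

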## **10.0 Statistical Considerations**

### **10.1 Power Analysis and Sample Size Calculation**

#### **D.3.c. Sample size calculation for Aims 1 and 2.**

$\beta$ -cell function, glucagon suppression, and IL-33 signaling are the primary outcomes for the aims. Sample size was calculated using a 2-group t-test with PS Software (version 3.0, Dupont&Plummer, 2009) at a 0.05 two-sided significance level. We estimate a 50% incidence of PTDM by day+100 (1, 8, 14). The sample size provides at least 80% power to detect a biologically meaningful difference in mean between patients with and without PTDM for each aim. The same patient cohort will be monitored for all aims. We will enroll 34 patients to ensure at least 80% power for each aim. Assuming the dropout rate is about 10% (early death or pre-HCT diagnosis of diabetes by OGTT), an additional 6 subjects will be recruited (41-43). Forty subjects are feasible to accrue over 4 years, given that 151 patients underwent allogeneic HCT at Vanderbilt in 2015.

**Subaim 1A primary outcome: second-phase GSIS.** A mean difference of 7.5  $\mu$ U/mL represents a significant difference in second-phase insulin release between healthy controls and individuals at risk for type 2 diabetes (44-46). A sample size of 17 patients in each group (either with or without PTDM) has 80% power to detect at least a 7.5  $\mu$ U/mL difference in insulin secretion between groups using a standard deviation of 7.5  $\mu$ U/mL.

**Subaim 1B primary outcome: glucagon secretion during OGTT.** AUC was calculated for each patient to present as total glucagon secretion during OGTT. Our preliminary data observed  $8.83 \pm 0.73$  pg/mL•min (mean  $\pm$  SD) in log(AUC) scale for patients with PTDM (Figure 4). With a sample size of 9 each group, there is 80% power to detect a log(AUC) change of from 8.83 pg/mL•min to 7.83 pg/mL•min.

**Aim 2 primary outcome: IL-33 signaling** Extrapolating our preliminary and pre-clinical data, a mean difference of 70 pg/mL is likely to represent a significant difference in IL-33 signaling between groups (14, 20). With a sample size of 17 in each group, there is 80% power to detect a 70 pg/mL difference in IL-33 production between groups using a standard deviation of about 70 pg/ml.

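### Section 10.1 promises at least 80% power at 34 patients from a t-test, but section 10.2 names the Wilcoxon test for Subaim 1A, which gives slightly less with normal data; the 1B line is also about 2 points high if its SD applies to both groups

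*Combined protocol and SAP*

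**What the plan says.** All sizing is in section 10.1 of the combined protocol and SAP. "Sample size was calculated using a 2-group t-test" at a two-sided 0.05 level. On group sizes: "We estimate a 50% incidence of PTDM by day+100". On the cohort: "The same patient cohort will be monitored for all aims". The headline is "We will enroll 34 patients to ensure at least 80% power for each aim". For about 10% dropout, "an additional 6 subjects will be recruited", which makes 40.

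- **Subaim 1A:** difference 7.5 µU/mL, SD 7.5 µU/mL, 17 per group, 80% power.
- **Aim 2:** difference 70 pg/mL, SD about 70 pg/mL, 17 per group, 80% power.
- **Subaim 1B:** the mean and SD, 8.83 ± 0.73, are given "in log(AUC) scale for patients with PTDM" only. The line then reads "With a sample size of 9 each group, there is 80% power to detect a log(AUC) change", from 8.83 to 7.83.

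Section 10.2, under the primary analysis of Subaim 1A, assigns the Wilcoxon rank sum test and describes it as comparing population means. It says that 1B and Aim 2 will be approached similarly, without naming a test for them. The general statistical plan in the same section permits a two-sample t-test or a Wilcoxon test for any two-group comparison of a continuous variable.

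**The concern.** The stated power belongs to one test and the named 1A primary analysis is another. With normal data the rank sum test is slightly less powerful than the t-test, and at 17 per group the t-test clears 80% by only 0.7 of a point. A promise that 34 patients secure at least 80% may therefore not carry over to the named analysis.

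PTDM status is also an outcome observed up to day +100, not an allocated group, so an even split is an expectation and not a design feature. Finally, the 1B line should follow from its own inputs by the stated t-test. At stake are the accuracy of the printed power figures and having one primary test fixed in advance.

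**Working it through.** **Inputs (section 10.1).** Two-sided 0.05; standardised difference d = 7.5/7.5 = 1 for 1A and 70/70 = 1 for Aim 2; PTDM incidence 50%; 40 recruited, so 40 × 0.9 = 36 evaluable expected. Having only 34 evaluable means losing 6/40 = 15%.

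**Step 1: the plan's own figure.** t-test power comes from the noncentral t distribution with n1 + n2 − 2 degrees of freedom and noncentrality d·√(n1·n2/(n1 + n2)). At 17/17 the noncentrality is √(289/34) = √8.5 = 2.92, giving 80.7%. The stated 80% reproduces. Uneven splits of 34 give 80.6% at 16/18, 80.2% at 15/19 and 79.5% at 14/20.

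**Step 2: the test named in section 10.2.** Wilcoxon power was simulated with normal data, a shift of 1 SD and exact critical values (200,000 runs per fixed split).

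**Step 3: group sizes left to chance.** Power at each split was averaged over a Binomial(N, 0.5) number of PTDM patients.

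| Setting (d = 1, normal data) | t-test | Wilcoxon |
|---|---|---|
| 17/17 fixed | 80.7% | about 78.4% |
| 18/18 fixed | 83.0% | 80.3–80.4% |
| 34, chance split | 79.5% | 76.4% |
| 36, chance split | 81.9% | 79.5% |

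With 37 evaluable, chance-split Wilcoxon power is about 80.6%. Using the normal approximation instead of exact critical values moves the 36-patient figure only within 79.1–79.6%.

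**Step 4: what makes up the drop at 34.** From 80.7% to 76.4% is 4.3 points. Changing the test at 17/17 costs 80.7 − 78.4 = 2.3 points; letting the split vary costs a further 78.4 − 76.4 = 2.0 points. About half of the drop is therefore not due to the test.

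**Step 5: sensitivity.** At 60% PTDM, the incidence in the 84-patient cohort of section 3.0, chance-split Wilcoxon power is about 74.5–74.7% at 34 and 77.5% at 36. The documents give no distribution, so the following shapes are assumptions, run at 50% PTDM:

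| Shape (Wilcoxon, chance split) | 34 | 36 |
|---|---|---|
| Uniform | 72% | 75% |
| t with 5 degrees of freedom | 84% | 87% |
| Lognormal, log-SD 0.5 | 89% | 91% |

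**Step 6: the 1B line.** The difference is 8.83 − 7.83 = 1.0. Assuming SD 0.73 in both groups, d = 1/0.73 = 1.37. At 9 per group the noncentrality is 1.37 × √(81/18) = 2.91 and t-test power is 77.9%; at 10 per group it is 82.5%. The printed 80% at 9 needs a common SD of about 0.711, that is, about 0.69 in the other group if PTDM patients have 0.73. A normal-approximation formula does return 9 per group (82.8%), but the stated method is a t-test. In the shared cohort of 34 to 36 with chance splits, 1B power is 96.8–97.5% by t-test and 95.6–96.7% by Wilcoxon.

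**The case against.** The strongest reply is that section 10.1 contains no arithmetic error for 1A: it names its planning test, and its figure reproduces. The planned surplus also nearly absorbs the change of test. The usual large-sample inflation for Wilcoxon with normal data, π/3, turns 34 into 35.6, and 36 evaluable are expected. At 18/18 the Wilcoxon test passes 80%. Planning at the expected split is ordinary practice, and the 76% figure needs both random splits and a 15% loss. The direction also depends on shape: glucagon AUC is planned on a log scale and the general plan foresees transformations, so skewed data are contemplated, and there Wilcoxon may exceed 80%.

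All of that stands, and it limits the size of the point. It does not rescue the wording. The promise is attached to 34 patients, and even at an exact 17/17 split the named 1A test gives about 78% under the section's own mean and SD with normal data. If skewness is the reason for choosing Wilcoxon, the plan does not say so.

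A reader might infer three stronger things that the documents do not support:

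- **That the study is underpowered and needs more patients.** At the expected 36 the gap is about half a point.
- **That the whole fall to 76% is the price of the Wilcoxon test.** The t-test also drops below 80% at 34 once splits vary.
- **That Wilcoxon is fixed for 1B and Aim 2.** Section 10.2 promises only a similar approach, after sentences on logistic regression, and the general plan allows either test. Applying the Wilcoxon figures to Aim 2, or about 72% at 9 per group to 1B, is an inference.

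**Conclusion.** The point holds as a minor correction. The assurance of at least 80% power at 34 patients is true for the t-test at an even split, but not for the Wilcoxon test named for 1A when data are normal and the difference is 1 SD. The gap to 80% is about 1.6 points at 17/17, about 3.6 points at 34 with chance splits, and about 0.5 point at the expected 36. These sizes assume normal data and 50% PTDM; they grow somewhat at 60% PTDM and can vanish or reverse with skewed or heavy-tailed data.

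The 1B line is 80 − 77.9 = 2.1 points too high by the stated t-test, but only if SD 0.73 also applies to patients without PTDM, which the plan does not say. It has no bearing on study size.

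**What to change.** 1. Name one primary test for each of 1A, 1B and Aim 2, and use it consistently in section 10.1, the primary analysis text of section 10.2 and the general statistical plan.
2. Replace the assurance of at least 80% with the power of that test and its assumptions. If Wilcoxon: about 78% at 17/17 and about 79.5–80% at the expected 36, with normal data. If the t-test: about 81% at 17/17 and about 82% at 36.
3. If Wilcoxon is kept, describe its target as a location shift instead of a difference in population means.
4. Restate the 1B line as about 78% at 9 per group, or 10 per group for 80%, by t-test. Say that a common SD of 0.73 is assumed and that the shared cohort gives 1B about 96–98%. If Wilcoxon is confirmed for 1B, compute the line for that test instead.

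The cost is wording only, with no added patients, visits or samples. The downside is that a printed figure becomes slightly less favourable and, under Wilcoxon, rests on an explicit normality assumption.
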